#### **2. Précis/Abstract:**

Cytokines released by an activated immune system have been associated with decreased brain dopamine and the development of depression, which afflicts over 20 million adults in the United States. Biomarkers of inflammation, such as inflammatory cytokines and acute-phase proteins like C-reactive protein (CRP), are reliably elevated in a significant proportion of patients with mood and psychiatric disorders. Our recent findings using functional magnetic resonance imaging (fMRI) indicate that depressed patients with high inflammation (defined as plasma CRP  $>3$  mg/L) exhibit reduced connectivity between the striatum and prefrontal cortical brain regions, which associate with symptoms of reduced motivation or anhedonia, a core symptom of depression. The striatum is a key subcortical structure that sends and receives multiple projections to and from the frontal cortex and other brain regions to regulate motivation, and dopamine plays a key modulatory role. Therefore, inflammation-related decreases in striatal dopamine may influence corticostriatal connectivity to mediate symptoms of anhedonia. Our non-human primate work has revealed that inflammatory cytokine effects on striatal dopamine can be reversed by administration of the dopamine precursor, levodopa (L-DOPA). However, whether administration of L-DOPA in humans can reverse inflammation-related disruptions in corticostriatal connectivity and anhedonia is unknown. This study will test the hypothesis that administration of L-DOPA to depressed patients with high inflammation will 1) increase functional connectivity between the striatum and prefrontal cortical brain regions, and 2) improve objective measures of motivation compared to placebo. Medically healthy, medication free depressed patients will be recruited to ensure a range of inflammation from low to high (as determined by plasma CRP) and will undergo resting state fMRI before and after administration of low dose L-DOPA-carbidopa (250/50 mg) and placebo on separate, double blinded visits. This within subject, crossover design has been used previously in a similar study assessing the effects of L-DOPA on corticostriatal functional connectivity in healthy controls.(1) All subjects will undergo MRI scanning as well as neuropsychiatric assessments and blood sampling, when applicable, at baseline and before and after placebo or L-DOPA administration during 2 outpatient visits. This work will establish whether alterations in corticostriatal connectivity may serve as a sensitive and specific brain biomarker for the effects of inflammation on striatal dopamine, while providing supporting data for future studies exploring therapeutic strategies that facilitate availability of dopamine precursors in patients with anhedonia and increased inflammation.

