**Dependent variables:**

Neuroimaging: resting-state fMRI; arterial spin labeling (ASL); task-based fMRI (monetary incentive delay)

Immune Markers: Plasma CRP

**Objective 2: To examine whether L-DOPA-mediated increases in corticostriatal connectivity are associated with improvement in objective measures of motivation and motor performance.**

**Hypothesis 2:** L-DOPA administration will be associated with improvement in motivation and psychomotor speed compared to placebo, and will correlate with increased corticostriatal connectivity.

Patients described in Objective 1 will undergo performance-based assessments of motivation and motor performance, and self-report assessments of depressed mood, including anhedonia, following administration of L-DOPA and placebo, which will be correlated with changes in functional connectivity.

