
treatment. Additional CRP testing, psychiatric assessments, or medical assessments may be conducted as indicated by the PI, study physician or PI's designee. Prior to each MRI neuroimaging session, patients will undergo a urine toxicology screening (Testcup for drugs of abuse, or equivalent as approved by PI or PI's designee) for safety and exclusion of substance abuse. On the last screening visit, patients will undergo blood sampling in the morning (collected at the same time as blood draw for safety labs and/or CRP), and complete neurocognitive testing. During Study Visits 1 & 2, subjects will complete a series of self-reports in the morning, have MRI scans (including resting-state fMRI and ASL) pre- and post-L-DOPA or placebo administration from about 9 AM to 12:30 PM, and undergo blood sampling and selected neurocognitive testing after the MRI scans from about 12:30 to 2 PM. L-DOPA or placebo, which will be administered double-blind (randomized by the Emory IDS), will be administered in the waiting area of the Neuroimaging Facilities. Patient's vital signs will be monitored by a Study Physician or designated Nurse Practitioner before, during, and after drug administration. At each study visit, 6 ml of research blood will be collected at 4 degree for extraction of plasma to measure inflammatory markers and/or L-DOPA concentrations. Two 3 ml samples will be collected (at the screening visit #2 only) for whole blood mRNA gene expression. 2 buffy coat samples from the first research blood collected for plasma (screening visit #2) will also be stored for genetic analyses of relevant gene polymorphisms and DNA methylation. In order to further assess immune cell profiles, we will also collect 10 ml of whole blood in EDTA at room temperature for immune cell extraction. Some samples may be sent to other labs for additional analysis. Safety laboratory tests will be conducted at screening, which will include a hematocrit (CBC with automated differential), electrolyte panel (comprehensive metabolic panel), urinalysis with microscopic, and serum quantitative pregnancy test (for women only). A CRP test will be completed at both screening visits to establish stability, and may be repeated during study visits at the PI's or PI's designee's discretion. Subjects who smoke cigarettes must refrain from smoking 30 minutes before all blood draws and 2 hours prior to mRNA sampling. Subjects who smoke half a pack per day, or e-cigarette equivalent, will be offered a nicotine patch during study visits to reduce the effects of withdrawal on fMRI scans.

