  - h) urinalysis with microscopic
  - i) serum quantitative pregnancy test (if female)
  - j) urine toxicology for drugs of abuse
  - k) Pt/INR (only done if S will be participating in the LP procedure)
  - l) PTT (only done if S will be participating in the LP procedure)

Procedures	Initial Visit	Screening #1†	Screening #2†	Lumbar Puncture Visit	Additional (If needed)	Study Visits #1-3
Consent/re-consent	X	[X]	[X]	[X]	[X]	[X]

Physical exam		X	[X]		[X]	[X]
Health update and vitals			[X]	[X]		[X]
Concomitant Medications		X	X	X	[X]	X
Adverse Events		X	X	X	[X]	X
History of Chronic Conditions		X			[X]	
CRP	[X]	X	[X]	[X]	[X]	[X]
Safety Labs #	[X]	X	[X]	[X]	[X]	[X]
Additional Safety Labs ##	[X]	[X]	[X]	[X]	[X]	[X]
Pt/INR, PTT (for LP only)	[X]	[X]	[X]	[X]	[X]	[X]
Research blood draws †		[X]	X	[X]	[X]	X
MRI Scan						X
Neurocognitive tests		[X]	X	[X]	[X]	
Neurocognitive tests *				[X]		X
Psychiatric Assessments Y	X	[X]	[X]	[X]	[X]	[X]
Psychiatric Assessments YY		X	[X]	[X]	[X]	
Psychiatric Assessments YY Y				[X]		X
Self Reports	X	[X]				
Self Reports *			X	[X]	[X]	
Self Reports **						X
MRI Scan Food, Drink and Cigarette Intake Form +						X
Lumbar Puncture				X		
Placement of ECG patches		[X]	[X]		[X]	

[X]: To be completed when indicated.

† Screening 1 & 2 can be completed on the same day if preferred by patient

#Safety Labs: Complete Metabolic Panel, CBC w diff, Serum Preg Test (females), Urinalysis w micro, Urine drug test

##Additional Safety Labs (screening #1 or screening #2): HIV Ag/Ab, Hep B Ag, Hep C Ab, ANA, TSH, Glycosylated Hemoglobin, EKG, Chem 7: electrolytes, urea, creatine, glucose, and/or hsCRP

Pt/INR, PTT to be completed for subjects who consent to LP within 2 weeks of procedure at any visit

‡ To be completed at one of the two screening visits during collection of safety labs and/or screening CRP

Neurocognitive tests: EEFRT, TMT-A, TMT-B, Digit Symbol Task, FTT, Reaction Time Task, Choice Reaction, Delayed Matching to Sample, Spatial Working Memory, RAVLT, Stroop word and color test to be completed at the end of the last screening visit

Neurocognitive tests\* (Visits 1 & 2): EEFRT, TMT-A, Digit Symbol Task, FTT, Reaction Time Task

Y Psychiatric Assessments (Initial Visit): PHQ-9 or QIDS

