### **Neurocognitive Assessments:**

A range of neuropsychological assessments will be used to probe basal ganglia function and will be associated with inflammation status as noted above. Assessments will lie along a continuum, progressing from more purely motor tasks (such as finger tapping) which assess circuitry within the basal ganglia to those that involve motor speed with increasing cognitive demand and cortical participation (e.g. the Digit Symbol Task). In addition, we will administer a test of procedural memory, with minimal processing speed or reaction time demands, that has been shown to be sensitive to dysfunction in the basal ganglia, without the executive demands associated with tests of frontal lobe function. Every effort will be made to match groups on the basis of demographic factors affecting test performance, such as age, education level, gender and ethnicity. These factors can significantly influence neuropsychological test results and while relatively small variations between groups can be handled through addition of covariates to statistical analyses, more significant differences in group composition will threaten the integrity and interpretation of the results.

**Finger Tapping Task (FTT):** This task uses a specially adapted tapper that the subject is asked to tap as fast as possible using the index finger. The subject is given 5 consecutive 10-second trials for both the preferred and non-preferred hands. The finger tapping score is the mean of the 5 trials and is computed for each hand. Performance norms have been established, and scores have been shown to be stable over time (84). The FTT is designed to assess subtle motor impairment and has been found to be altered in subjects with basal ganglia disorders and lesions (85).

**Reaction Time Task (CANTAB):** The reaction time test includes simple and choice reaction time tasks and is

divided into 5 stages requiring increasingly complex chains of responses and providing distinction between reaction (or decision) time and movement latencies. Movement times on the CANTAB reaction time task have been shown to be slowed during IFN- $\alpha$  treatment and correlate with IFN- $\alpha$ -induced depression and fatigue (see Preliminary Results). Moreover, reduced DA transmission, as indicated by increased binding of the dopamine D2/3 ligand I-ZBM in the striatum, has been correlated with motor slowing in the CANTAB reaction time task in depressed patients (86).

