**Baseline Assessments:** During screening, a research blood sample (18 ml total) may be collected along with blood draw for safety labs and/or CRP measurement. Research blood will be used for measurement of plasma inflammatory markers, mRNA gene expression for inflammatory signaling pathways, circulating and mRNA gene expression markers related to metabolism and endocrine hormones, and buffy coat to examine polymorphisms in relevant inflammatory proteins. For female subjects, questions pertaining to menopausal status will also be obtained using a Staging System for Reproductive Aging questionnaire. All patients will also complete a Composite Vascular Risk Profile Scale. A complete series of neurocognitive testing may also be performed during the last screening visit or the LP visit. The baseline research blood and neurocognitive assessments are necessary to complete prior to randomization to study treatment. They may be collected along with screening assessments that are being conducted to determine eligibility for the LP procedure or randomization to study drug, or at the LP visit. Physiological measures including heart rate and activity may also be recorded using adhesive ECG patches. These data may also be used independently of qualification for further study participation. To reduce patient burden, a 15 minute break will be given in between motivational and motor assessments. Participants will receive \$25 for this visit, an additional \$25 if research blood is collected, and an additional \$25 if ECG patches are placed. Patients will also receive \$50 for completing motor and motivational assessments, and up to \$60 for completing the EEfRT based upon the subject's responses.

**ECG patches for collection of biometric data (optional):** Patients will be given the option of wearing ECG patches (MC10 BioStamp®) to record physiological measures including heart rate and activity. Trained members of the study team will place the ECG patches on the chest of the subject and they will record heart rate and activity over 24 hours. Another patch may need to be placed on the subject's leg; the subject will be trained to do this themselves. These patches will be returned to the study team either at the next study visit or by a pre-paid envelope that will be provided to the subject.

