**Analytic Strategy, Objective 1:** The primary outcome will consist of a targeted, hypothesis-driven approach including extraction of individual patient level Z scores for connectivity with ventral or dorsal striatum and regions of interest identified in our previous work that 1) exhibited alterations in connectivity between patients with high and low inflammation, and 2) were significantly associated with behaviors of interest. Post-L-DOPA or placebo administration Z scores will be entered into linear models controlling for pre-administration connectivity scores as well as relevant covariates. The difference (delta; post minus pre) in connectivity Z scores before and after placebo and L-DOPA will also be compared by paired T test, and between patients with high and low inflammation (CRP > or < 3mg/L). Generalized linear mixed model (GLMM) will be used to assess whether corticostriatal connectivity is improved by L-DOPA, and whether effects depend on concentrations of CRP, while controlling for clinical and demographic covariates. Linear regression models will be used to determine whether increased CRP is associated with decreased response to hedonic reward, as assed at by fMRI using the MIDT. Response to hedonic reward (as measured by MIDT) will also be used to assist in interpretation of resting-state connectivity data before and after L-DOPA administration in two ways: 1) Striatal regions activated in response to reward will be used to corroborate location of the striatal seed regions for resting-state connectivity analysis, and 2) responses to the MIDT will be entered into GLMM models to determine whether decreased reward sensitivity predicts greater increase in connectivity after L-DOPA. White matter integrity as measured by DTI will also be used to assist in interpretation of responses to L-DOPA, as subjects with less cortical-striatal-thalamic anatomical connections may have less ability to respond to increases in dopamine. To identify other corticostriatal circuits that may be affected by increasing dopamine precursor, striatal seed-to-whole-brain comparisons of L-DOPA versus placebo, will be performed as a secondary analysis strategy. In the event that CRP fails as a classification or correlational variable, exploratory analyses will be conducted using other measures of inflammation described above for Objective 1.

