**Analytic Strategy, Objective 2:** Similar to the analytic strategy for Objective 1, post-L-DOPA or placebo administration neurocognitive performance or self-report scores will be entered into linear models with CRP (or other inflammatory markers) while controlling for pre-administration behavioral scores as well as relevant covariates. The difference (delta; post minus pre) in behavioral scores before and after placebo and L-DOPA will also be compared by paired T test, and between patients with high and low inflammation (CRP > or < 3mg/L). L-DOPA-related changes in functional connectivity in Objective 1 will then be compared to relevant post-LDOPA task-based and self-report behavioral responses using linear modeling.

**Analytic Strategy, Objective 3:** Relationships between functional connectivity and behavior before and after L-DOPA with central and peripheral inflammatory cytokines and their soluble receptors, and biomarkers of their potential effects on dopamine through decrease BH4 activity will be explored. Gene transcripts associated with inflammatory and metabolic signaling pathways related to inflammation effects on the brain have been used to predict response to pharmacological therapies (54, 95), including our previous work (96, 97). Therefore, genome-wide gene expression will be assayed. Plasma and CSF will be collected on a separate visit to measure IL-6, IL-1 $\beta$ , TNF and their soluble receptors, CSF BH4, dopamine, HVA and DOPAC, and plasma phenylalanine and tyrosine. Linear regression will be used to examine relationships between functional connectivity Z-scores or behavior (dependent variables) and biomarkers of inflammation and dopamine synthesis (independent variables), while controlling for covariates. Cytokines and their receptors will be examined first independently (with and without correction for multiple comparisons), then together in models to identify biomarker(s) that are most significant after backward and forward linear regression. If variables are collinear (as assessed by variance inflation factor, tolerance and leverage plots), principal component analysis (PCA) will be used.(98) Gene expression that correlates with CRP, or differs between patients with

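### Objective 2's paired t-test has no visit term: if the behavioural baseline is taken once, before randomisation, adding one protects power on the timed performance tests at almost no cost

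*Combined protocol and SAP*

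**What the plan says.** The analysis in question is in section 7, Analytic Strategy, Objective 2: "The difference (delta; post minus pre) in behavioral scores before and after placebo and L-DOPA will also be compared by paired T test". It comes second. The same paragraph first enters post-administration scores into linear models with the pre-administration score and covariates that it calls relevant but does not define. The list of demographic and illness-related covariates at the end of section 7 names neither visit nor order, though it is worded as optional and does not close the set. The generalised linear mixed model is named only under Objective 1, fitted "while controlling for clinical and demographic covariates".

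On timing, the documents point two ways.

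- **One baseline, then one session per dosing visit.** Section 4 (Objective 2) places "performance-based assessments of motivation and motor performance, and self-report assessments of depressed mood, including anhedonia, following administration of L-DOPA and placebo". The Study Overview in section 5 has patients "undergo blood sampling and selected neurocognitive testing after the MRI scans from about 12:30 to 2 PM". The footnotes to the procedures table list the tests at Visits 1 and 2 as "EEFRT, TMT-A, Digit Symbol Task, FTT, Reaction Time Task" and put the full battery at the end of the last screening visit. The Baseline Assessments paragraph adds: "The baseline research blood and neurocognitive assessments are necessary to complete prior to randomization to study treatment".
- **Possibly a pre-dose test at each visit.** The Précis describes assessments, where applicable, "at baseline and before and after placebo or L-DOPA administration during 2 outpatient visits". The Objective 2 paragraph itself speaks of pre-administration scores and of deltas before and after each treatment.

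**The concern.** Every patient takes the same performance tests at both dosing visits, with L-DOPA at one and placebo at the other. If scores improve from Visit 1 to Visit 2 through practice, each patient's L-DOPA-minus-placebo difference contains that gain, with a plus sign if L-DOPA came second and a minus sign if it came first. A single baseline shared by both conditions subtracts out and cannot remove it.

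A paired t-test treats this order-driven spread as noise. With equal orders the gain cancels from the mean but inflates the standard error. With unequal orders it also moves the estimate by chance. The stake is precision in the one Objective 2 analysis whose L-DOPA versus placebo contrast is spelled out.

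The concern is confined to tests with an evident practice mechanism: Trail Making A, Digit Symbol, Finger Tapping and Reaction Time. The effort task (EEfRT) measures a choice between difficulty levels, so it belongs here only if a practice effect on that choice is plausible. Self-reports have no evident practice mechanism.

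**Working it through.** **The plan's own figure.** The only power statement (section 7, Power Analysis) concerns connectivity: a standardised paired effect (dz) of about 1, n=30 per group, alpha 0.05, power above 80%. An exact two-sided paired-t calculation gives 99.96% at n=30 and 99.88% at n=27, so the statement holds as a lower bound. No power is given for Objective 2.

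**Inputs from the documents.** 80 patients analysed; two-sided alpha 0.05; about 27 patients per CRP stratum; two dosing visits in randomised order, with ratio and blocking not stated.

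**Assumptions.** A further Visit 1 to Visit 2 gain π of 0, 0.25, 0.5 or 1.0, in units of the SD of the paired difference within an order; 1:1 order.

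**Model.** D = τ + sπ + e, where D is L-DOPA minus placebo, s = +1 if L-DOPA is at Visit 2 and −1 otherwise, and e has SD 1. The paired t-test uses a variance of about 1 + π². The period-adjusted estimate is the mean of the two order-specific means and uses a variance of 1. The effect τ = 0.317 gives 80% power at n=80 when π = 0.

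**Main contrast, n=80, order 40:40** (40,000 simulated trials per cell):

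| Gain π | Paired t power | Power with visit term | Paired t type I error | 80/(1+π²) |
|---|---|---|---|---|
| 0 | 80.0% | 80.0% | 4.9% | 80 |
| 0.25 | 78.0% | 79.8% | 4.3% | 75.3 |
| 0.5 | 72.8% | 80.1% | 2.8% | 64.0 |
| 1.0 | 50.6% | 79.9% | 0.5% | 40.0 |

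**Hand check at π = 0.5.** The true SE is 1/√80 = 0.1118. The SE used by the paired test is √[(1 + 0.25 × 80/79)/80] = 0.1252. The rejection threshold is 1.990 × 0.1252 = 0.249. Power is approximately Φ[(0.317 − 0.249)/0.1118] = Φ(0.61), or about 73%.

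**Simple randomisation, n=80.** At π = 0.5, paired power is 70.3% against 79.3% with the visit term, and the paired test's type I error is 4.9%. Mean bias is within 0.001 SD. In a single trial the estimate shifts by π(n₁ − n₂)/n: with orders 44:36 and π = 0.5, that is 0.5 × 8/80 = 0.05 SD.

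**CRP contrast** (above versus below 3 mg/L, 27 versus 54, simple randomisation, effect set for 80% adjusted power). Without a visit term, power is 78%, 71% and 51% at gains of 0.25, 0.5 and 1.0; with it, 79–80%. Type I error without the term is 5.1%, 4.9% and 5.0%.

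**Dependence on pre-score timing** (n=80, gains 0/0.25/0.5/1.0). With a shared pre-randomisation baseline, paired power is 80.0/78.1/73.1/50.6%. With a same-visit pre-dose baseline it is 79.8/79.8/80.1/80.3%, because a constant visit shift cancels within each delta.

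**Cost when there is no gain.** Essentially nothing with balanced orders. Under simple randomisation, about 0.5 points at n=80 (80.1% to 79.6%) and 1.6 points at n=27 (79.8% to 78.2%).

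**The case against.** The strongest reply concerns weight. The paired test is supplementary, the linear models could take visit as one of their undefined covariates, no power is claimed for Objective 2, and the plan calls the project a pilot. The wording of the Objective 2 paragraph can naturally be read as a pre-dose score for each condition, and on that reading there is nothing to recover. The gain is also unknown: all five tests are in the screening battery, so Visit 1 to Visit 2 is at least a second-to-third exposure, and for finger tapping the protocol says that "scores have been shown to be stable over time". At a gain of 0.25 SD the loss is about 2 points, close to the 1.6 points that a visit term can cost at n=27.

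All of that stands, and it limits the point to a conditional improvement. It does not remove it. Leaving room for visit in the linear models is not the same as naming it, a paired t-test cannot hold the term at all, and the detailed schedule supports one session per dosing visit. At n=80 the trade favours the term: at most about half a point lost if there is no gain, against about 7 points recovered at 0.5 SD with balanced orders.

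A reader might infer more: that practice effects bias the L-DOPA effect or inflate false positives. The documents do not support this. Order is randomised, so the gain averages out, and type I error stays near 5% under simple randomisation or falls below it when orders are balanced. Nor does the point reach connectivity, where the pre-dose scan at each visit removes a constant shift, or the stated power above 80%.

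**Conclusion.** The point holds as a near-free improvement, conditional on the behavioural pre score being a single pre-randomisation baseline. On that reading, a practice gain between the dosing visits costs the paired test power: from 80% to about 78% at 0.25 SD and to about 73% at 0.5 SD, with n=80 and order 40:40. The 1.0 SD row (51%, equivalent to 40 of 80 patients) is a pessimistic bound, because the tests were already taken at screening, and should not be quoted as the expected loss. All these sizes rest on assumed gains. The harm is lost power, plus a chance shift if the orders turn out unequal; Objective 2 is not invalidated. If each dosing visit has its own pre-dose test, a constant visit shift cancels and only the need to clarify the wording remains. A visit term does not address carryover, which is a separate matter.

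**What to change.** 1. For the repeated performance tests (Trail Making A, Digit Symbol, Finger Tapping, Reaction Time, and EEfRT if a practice effect is thought plausible), make the L-DOPA versus placebo comparison a period-adjusted crossover contrast, in place of or beside the paired t-test. Use a mixed model with fixed treatment and visit and a random patient effect. For the CRP question, add treatment × CRP with the CRP main effect.
2. State when the behavioural pre score is taken. Reconcile the Précis and the Objective 2 analysis paragraph with section 4 (Objective 2), the Study Overview, the procedures-table footnotes and the Baseline Assessments paragraph.

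The cost is one degree of freedom and one or two sentences in the analysis plan. No new data are needed and patients are not affected. Specifying the term before unblinding also avoids a later choice between adjusted and unadjusted results.
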